Rationale: The REspiratory Syncytial virus Consortium in EUrope (RESCEU) is an Innovative Medicine Initiative (IMI) funded by the EU and EFPIA under the H2020 framework to define and understand the burden of disease caused by human respiratory syncytial virus (RSV) infection. RSV causes severe disease in individuals at the extremes of the age spectrum and in high risk groups. It was estimated that RSV was associated with 34 million cases of acute respiratory tract infection (ARTI), 3.4 million ARTI hospitalizations and 55,000 to 199,000 deaths in children <5 years in 2005 worldwide. The estimated burden of disease in older adults is comparable with non-pandemic influenza A (for which a vaccine is available). These estimates were based on limited data and there is a substantial gap in knowledge on morbidity and associated healthcare and social costs in Europe. New vaccines and therapeutics against RSV are in development and could soon be available on the European market. RESCEU will deliver knowledge of the incidence and burden of RSV disease in young children and older adults in Europe, which is essential for stakeholders (governments, etc.) to take decisions about prophylaxis and treatment.

Objective: To determine the burden of disease due to RSV in older adults.

Study design: Prospective epidemiological, observational, multi-country, multicenter cohort study.

Study population: Adults aged 60 years and up (n= approximately 1,000).

Main study parameters/endpoints:

The primary endpoints of the study are;

- RSV associated medically attended (MA) ARTI.
- RSV related hospitalization.
- The incidence of RSV infection-associated ARTI.

Nature and extent of the burden and risks associated with participation, benefit and group relatedness:

A blood sample (60 ml) and a nasopharyngeal swab will be collected at the beginning (August/September) and end (May/June) of the RSV season. The drawing of blood can be moderately painful. The collection of a nasopharyngeal swab can cause a brief moment of discomfort. Participants will be asked weekly by telephone (verbal or text message), email or telephone app about any signs of respiratory tract infections. In the event of an ARTI two nasopharyngeal and one oropharyngeal swab will be collected to perform a direct reverse transcriptase polymerase chain reaction (RT-PCR) for RSV and additional analyses if RT-PCR is positive for RSV. If a participant experiences a RSV positive ARTI, blood will be drawn (60 ml) and a nasopharyngeal swab will be collected at the time of the infection and 1-2 weeks after onset of symptoms. During the course of each ARTI, independent of RSV status, participants will be asked to complete a short daily diary in order to score respiratory symptoms and quality of life. At inclusion and after approximately one year (+/- 2 months, at least after the RSV season) participants are asked to fill in a short questionnaire.

None of the RESCEU study procedures is associated with any risk for serious complications. However, there is a minimal risk of minor complications due to study procedures (for example a nose bleed after a nasopharyngeal swab or bruise after a blood test).

Possible benefit: There is no clear clinical benefit for the participants taking part in this proposed study. However, the results of this study aim to support the understanding of the burden of RSV disease, which is important for the implication of future preventive and therapeutic interventions.

1. INTRODUCTION AND RATIONALE

The RESCEU clinical cohort studies - summary

The IMI-funded REspiratory Syncytial virus Consortium in EUrope (RESCEU) programme includes an observational study to define the burden of disease caused by human respiratory syncytial virus (RSV) infection. A total of 4 clinical studies in specific risk groups will be performed in several European countries as part of the RESCEU study. The sites of these studies were selected because of their experience in acute respiratory tract infection (ARTI) and/or RSV research in specific risk groups.

[figure not shown]
The clinical cohort studies in young children (clinical study 1 and 2, fig. 1) will be conducted at the UMC Utrecht (Netherlands), University of Turku (Finland), Servicio Galego de Saúde (Spain), University of Oxford, University of Edinburg and Imperial College London (United Kingdom).

The clinical cohort study in older adults (elderly) (clinical study 3, fig.1) will be conducted at the UMC Utrecht (Netherlands), University of Antwerp (Belgium) and University of Oxford (United Kingdom).

The clinical cohort study in chronic obstructive pulmonary disease (COPD) patients (clinical study 4, fig. 1) will be conducted at the UMC Groningen (Netherlands) and Imperial College London (United Kingdom).

This protocol is restricted to Clinical Study 3.

Figure 1. Overview of clinical studies embedded in the RESCEU effort and follow up periods for included (individual) patients.

Version number: 3, July 29th 2019 6 of 27

Background

Human respiratory syncytial virus (RSV) causes severe disease in individuals at the extremes of the age spectrum and in high risk groups. It was estimated that RSV was associated with 34 million cases of acute respiratory tract infection (ARTI), 3.4 million ARTI hospitalizations and 55,000 to 199,000 deaths in children <5 years in 2005 worldwide. These estimates were based on limited data and there is a substantial gap in knowledge on morbidity and associated healthcare and social costs in Europe. RSV infection in childhood is associated with subsequent wheezing and asthma. These long-term sequelae pose a substantial additional burden on the healthcare system. In addition, RSV is a significant cause of ARTI morbidity in elderly and COPD patients. Most published data on RSV disease burden in the elderly (aged >65 years) are from the United States and from hospital settings and describe a disease burden similar to non-pandemic influenza A.

Treatment and prophylaxis options are limited. Mostly only supportive care is available for patients with severe RSV ARTI. Ribavirin has been used as treatment, but with limited evidence of benefit and is therefore not routinely recommended. Various new RSV vaccines and therapeutics could be available in the near future. To use these new vaccines and therapeutics in the best possible way and to guide their development and implementation, it is necessary to determine the burden of RSV disease in Europe to gain better insight in disease severity in young children and older adults and the associated societal and healthcare costs.

There is a parallel need to assemble clinical resources to identify the correlates of severe RSV disease for clinical management, classification of disease severity in clinical trials and identification of biomarkers for severe disease, which are currently lacking.⁸

For this purpose RESCEU (REspiratory Syncytial virus Consortium in EUrope) has been set up. RESCEU will perform the first prospective multi-center study in both older adults and children to provide accurate data on RSV disease incidence and sequelae (long-term airway morbidity, including asthma) and economic consequences of RSV infection.

The following document will describe only the protocol for the adult cohort study. The other prospective cohort studies are presented in separate protocols for these specific cohorts.

We will prospectively follow-up a cohort of approximately 1,000 older adults (\geq 60 years, of whom approximately 500 will be \geq 75 years) living in the community during one year to obtain incidence data on RSV infection, medically attended (MA) RSV infection and hospitalization due to RSV.

2. OBJECTIVES

 Table 1. Primary and secondary objectives and associated endpoints.

	Objectives	Endpoints
Primary	To estimate the incidence of RSV MA-ARTI in both inpatients and outpatients and overall RSV infection-associated ARTI in older adults.	Incidence rate of RT-PCR confirmed RSV infection-associated MA-ARTI in inpatients outpatients and overall RT-PCR confirmed RSV in older adults. Data collected by using samples, medical data from the hospital and questionnaires.
Secondary	To estimate the rate of all-cause MA (inpatient or outpatient) ARTI and related medical complications (exacerbations of chronic conditions, acute cardiovascular events).	Incidence rate of all-cause MA ARTI or events leading to worsening of cardiorespiratory status. Data collected by using diary, questionnaires.
	To estimate the RSV- associated and all-cause mortality.	 Mortality through the RSV season of follow up for RSV- associated deaths and all cause deaths. Data collected by using medical data from the hospital and questionnaires.
	To estimate health care costs, health care resource use, interruption of normal activities, and HRQoL in RSV-associated and all-cause MA (inpatient or outpatient) ARTI patients.	Health care costs and resource use, interruption of normal activities, and HRQoL in RSV-associated and all-cause MA (inpatient or outpatient) ARTI patients. Data collected by using diary, questionnaires.
	To estimate the incidence of RSV-related secondary bacterial pneumonia events and their association with antibiotic use within 21 days after onset of RSV infection.	Incidence rate of RSV- associated secondary bacterial pneumonia events (defined as pneumonia within 21 days after RSV infection) and associated antibiotic use. Data collected by using medical data from the hospital, diary and questionnaires.
	 To collect clinical samples for biomarker analysis on possible biomarkers which are predictive of 	Sample collection for biomarker analysis. Establish a Biobank for identifying potential biomarkers of

severe or complicated RSV disease in older adults. With these clinical samples a biobank will be established for identifying potential biomarkers of RSV disease severity for further validation.	RSV disease severity for further validation.
To examine the incidence of other respiratory pathogens associated with all MA-ARTI	 Incidence rate of other respiratory pathogens associated with all MA-ARTI. Data collected by using samples.
To estimate the proportion of viral ARTI attributable to RSV.	 Proportion of viral ARTI attributable to RSV. Data collected by using samples.
To estimate important risk factors for RSV infections (by severity and healthcare utilizations).	Important risk factors of RSV infection. Data collected by using baseline questionnaires.
To determine change in frailty over the course of the study	Change in frailty over the course of the study. Data collected by using diary, questionnaires.

3. STUDY DESIGN

[figure not shown]
This will be a multi-country, multicenter, prospective, observational cohort study conducted across 2 consecutive winter seasons to determine the incidence of RSV infection, RSV associated MA-ARTI and RSV related hospitalization in participants ≥60 years of age, recruited from the general population.

These older adults will be recruited from general practitioner (GP) networks between May and October of each year for 2 consecutive years based on pre-specified selection criteria (see section 4.2 and 4.3). Practice lists will be screened for potentially eligible participants. They will be informed by their GP about the study. If they consent that their contact details can be given to the study team, interested potential participants will be contacted by a member of the study team who will answer any questions they may have about the study. When participants are willing to be enrolled in the study, an inclusion visit is booked at the beginning of the RSV season (August/September). During the same visit a blood sample and a nasopharyngeal sample will be collected and a baseline questionnaire about demographic data, medical history, smoking habits and quality of life will be completed.

During the RSV season (October 1st to May 1st, or longer if RSV is still circulating, based on country specific surveillance reports), respiratory tract symptoms will be assessed weekly by telephone contact (verbal or text message), email, (daily) telephone app or online questionnaire. If the participant experiences an ARTI, the study team will visit the participant to collect two nasopharyngeal and one oropharyngeal sample for direct RSV RT-PCR and additional analyses. If RSV is positive a blood sample and nasopharyngeal sample will be obtained at the time of infection and an additional blood and nasopharyngeal sample will be collected 1-2 weeks after the onset of symptoms. At the end of the RSV season (May/June) another blood and nasopharyngeal sample will be collected. Individual participants will be followed up for one RSV season. After approximately one year (+/-2 months) participants will be asked to fill in a questionnaire to finalize follow-up. This questionnaire is about, but not limited to, respiratory disease in the past year, changes in living conditions, health status, frailty and quality of life.

An overview of the study design and main procedures is given below (Figure 2).

Figure 2. Overview of study design and main procedures of cohort of older adults.

4. STUDY POPULATION

4.1 Population (base)

Cohort of approximately 1,000 older adults (≥60 years, including approximately 500 ≥75 years). Participants will be randomly recruited from the database of general practitioners in the following countries: the Netherlands (UMCU), Belgium (UA) and United Kingdom (UOXF).

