4.4 Sample size calculation

For the primary analysis the ratio between cases of RSV-related hospitalizations and number of older adults in the total population will be calculated. In addition, the ratio between the cases of MA-RSV infection and the number of older adults undergoing active surveillance will be calculated.

To estimate the incidence of MA-RSV infection and RSV-related hospitalization at an older age, a prospective cohort of approximately 1,000 older adults ≥60 is followed for 1 year. For sample size calculations a statistic expert of the Julius Support Center was consulted. Assuming a yearly MA-RSV incidence of 3,0% based on literature^{5,9}, a sample size of 800 will produce a two-sided >95% confidence interval with a symmetric half width of 0.01 Version number: 3, July 29th 2019

(Confidence interval formula: Exact, Clopper-Pearson). Accounting for a 10% loss to follow up, approximately 1000 elderly will be included in the cohort.

Patient population	Sites	Outcome	Persons	RSV seasons	Expected Incidence per year (%)	95% Confidence Interval Half-Width (%)
Older Adults (≥ 60 years)	NL, UK, BE	Incidence rate of MA-RSV	1,000	1	3,0 ^{5,9}	1,9 – 5,0

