5.1.2 Secondary study parameters/endpoints

- The incidence rate of all-cause MA-ARTI or events leading to worsening of cardiorespiratory status. The incidence rate will also be summarized separately for outpatient events and for both inpatient and outpatient events combined through the RSV season of follow up. Subgroup analyses will summarize these endpoints by RSV season.
- 2. Mortality through the RSV season of follow up for RSV-associated deaths and all cause deaths.
- 3. Health care costs and resource use for RSV-associated and all-cause MA-ARTI (inpatient or outpatient) or events leading to worsening cardiorespiratory status with regard to hospital duration, incidence and duration of intensive care unit stay, supplemental oxygen use, antibiotic and antiviral use and number of outpatient visits (e.g., ER visit, physician office/outpatient visits) and HRQoL.
- The incidence rate of RSV-associated secondary bacterial pneumonia events (defined as pneumonia within 21 days after RSV infection) and associated antibiotic use will be summarized.
- 5. Change in frailty over the course of study.
- 6. Sample collection for biomarker analysis to investigate possible biomarkers which are predictive of severe or complicated RSV disease in older adults. With these

clinical samples a biobank will be established for identifying potential biomarkers of RSV disease severity for further validation.

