7. STATISTICAL ANALYSIS

Descriptive statistics will be used to describe the incidence rate of hospitalization for RSV and MA-RSV infection in the cohort of older adults. Demographic parameters, clinical parameters and outcome and laboratory test results will be displayed as categorical data with percentages or continuous variables with mean (+/-SD) and/or median (interquartile range).

Comparisons between groups will be performed using chi-square for categorical variables, Student-t-test for normally distributed continuous variables or Mann-Whitney U test for not normally distributed continuous variables. Multivariate regression analysis will be performed to analyse multiple risk factors for RSV disease.

Statistical analyses will be performed using SPSS version 20 or a more recent version or with R statistical software version 3.0.1 or higher.

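### About half the cohort is targeted at age ≥75, so the unweighted primary ratio estimates incidence in a 50:50 age mix, which matches the general ≥60 population only under conditions the protocol does not give

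*Protocol*

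**What the plan says.** Section 4.1 sets the composition: "Cohort of approximately 1,000 older adults (≥60 years, including approximately 500 ≥75 years". The Background in section 1 repeats the split. Section 4.1 continues: "Participants will be randomly recruited from the database of general practitioners in the following countries". It gives no sampling fraction by age.

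Section 3 gives the source and target: incidence "in participants ≥60 years of age, recruited from the general population".

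Section 4.4 states the primary measures. For hospitalisation, "the ratio between cases of RSV-related hospitalizations and number of older adults in the total population will be calculated"; I read the denominator as the whole study cohort. For medically attended (MA) RSV infection, "the ratio between the cases of MA-RSV infection and the number of older adults undergoing active surveillance will be calculated". Section 7 adds: "Descriptive statistics will be used to describe the incidence rate of hospitalization for RSV and MA-RSV infection in the cohort of older adults".

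Section 5.1.1 breaks the primary endpoint down by care setting. Age ≥75 appears in no objective, endpoint or analysis, although it shapes recruitment.

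**The concern.** The age target makes the sample's age mix a design choice. A simple ratio from such a sample averages the two age-specific rates with the weights of the design, here about one half each, and not with the weights of the population. If incidence, medical attendance or admission rises with age, the overall figure is too high for people ≥60 in general.

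The study exists to supply burden figures to those who decide on prophylaxis and treatment. A reader who multiplies the overall rate by a national ≥60 headcount would carry the design's age mix into the burden estimate. More participants would not reduce the error, and the confidence interval would not show it.

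The wording on recruitment adds an ambiguity. A simple random draw from GP lists reproduces the age mix of the lists. It gives about half ≥75 only if the lists are about half ≥75. Otherwise sampling must be stratified by age, and the protocol does not say so.

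**Working it through.** **Inputs from the protocol.** N about 1,000, about 500 aged ≥75 (section 4.1); expected MA-RSV incidence 3.0% for all ages ≥60, exact Clopper-Pearson interval, half-width 0.01 at n = 800 (section 4.4).

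**Inputs assumed, because the protocol gives neither.** Share s of the ≥60 population aged ≥75: 30–40%. Rate ratio r, ≥75 versus 60–74: 1.5–3.

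**Step 1: the plan's own precision.** At 3.0% the exact 95% interval is 1.93–4.43% for n = 800 (half-width 1.25 points) and 2.03–4.26% for n = 1,000 (half-width 1.11 points). The stated half-width of 1 point at n = 800 is not reproduced. That is a separate matter; here I only need the yardstick of about 1.1 points.

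**Step 2: age-specific rates implied by a crude 3.0% at 50:50.** With a the rate at 60–74, 0.5a + 0.5ra = 0.03, so a = 0.03/(0.5 + 0.5r).
- r = 1.5: 2.4% and 3.6%
- r = 2: 2.0% and 4.0%
- r = 3: 1.5% and 4.5%

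**Step 3: rate with population weights.** Standardised rate = (1 − s)a + s·ra. Relative overstatement = crude/standardised − 1 = (0.5 − s)(r − 1)/(1 + s(r − 1)).

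| s | r = 1.5 | r = 2 | r = 3 |
|---|---|---|---|
| 30% | 2.76% (+8.7%) | 2.60% (+15.4%) | 2.40% (+25.0%) |
| 35% | 2.82% (+6.4%) | 2.70% (+11.1%) | 2.55% (+17.6%) |
| 40% | 2.88% (+4.2%) | 2.80% (+7.1%) | 2.70% (+11.1%) |

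Worked cell: s = 35%, r = 2 gives 0.65 × 2.0% + 0.35 × 4.0% = 2.7%, against a crude 3.0%. The absolute gap over the table runs from 3.00 − 2.88 = 0.12 to 3.00 − 2.40 = 0.60 points.

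**Step 4: where it vanishes or reverses.** The numerator (0.5 − s)(r − 1) is zero at r = 1 or s = 50%. Below r = 1 the sign changes. For example, r = 0.5 gives rates of 4.0% and 2.0%; with s = 35% the standardised rate is 0.65 × 4.0% + 0.35 × 2.0% = 3.3%, and the crude 3.0% is then too low.

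**Step 5: price of weighting.** With 500 per stratum, standard error = √[(1 − s)²·p₁(1 − p₁)/500 + s²·p₂(1 − p₂)/500], where p₁ and p₂ are the rates at 60–74 and ≥75. Over the table, 1.96 standard errors come to 0.92–1.06 points, against 1.06 for the crude rate by the same normal approximation. At r = 1 they are 1.08–1.14. Precision is barely affected.

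**Step 6: precision of one stratum.** 15 cases in 500 (3%) gives an exact interval of 1.69–4.90%: wide, but reportable.

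**The case against.** The strongest reply is that the statistical analysis plan is not at hand, and age strata and standardisation are often left to it. Section 7 says only that incidence will be described; it does not call the rate single, crude or pooled, and it rules out no stratification. That is right about section 7. Section 4.4, however, does state the estimator for the primary analysis, as an unweighted ratio, beside a designed age mix. A later plan that standardised would still have to be reconciled with that text.

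Second, direction and size rest on two assumed quantities, and the gap is smaller than the sampling error. Both are true, and the conclusion is conditional for that reason. A systematic error below the interval half-width is still worth removing when it costs little.

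Third, weighting on two age groups would not by itself yield a general-population rate: section 4.3 excludes, among others, people with dementia or immunosuppression, and participants volunteer. This stands. Weighting removes one known distortion, not all of them.

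Some stronger readings are tempting but not supported:
- **A strict quota.** The text says approximately 500, which is a target; no cap or sampling fraction is stated.
- **Pooling over countries and two seasons as the same error.** No country or season allocation is fixed, so the sampling argument does not carry over. Section 5.1.2 foresees a season breakdown under its first secondary endpoint ("Subgroup analyses will summarize these endpoints by RSV season"). Doing the same for the primary endpoint is a reporting preference, and two separate season rates would not put season-to-season variation into the interval.
- **Weighting within each country.** At 3% of 1,000 there are about 30 MA-RSV cases, about five per cell over three countries and two age groups if spread evenly. That is too thin.

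**Conclusion.** The point holds in conditional form. As written, the primary ratio estimates incidence in a cohort about half of whom are ≥75. It equals incidence in the general ≥60 population only if people ≥75 make up about half of that population or incidence does not differ by age.

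A reader might infer that the study cannot estimate incidence in adults ≥60 at all. The documents do not support that: the two age-specific rates can be estimated from the planned data, and the overall figure needs only the right weights.

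Under the assumed shares and rate ratios a crude 3.0% is too high by about 4–25%. Outside those assumptions the overstatement can be nil or change sign. The range was worked at the MA-RSV planning rate; the same formula applies to hospitalisation, whose age gradient the protocol does not give either. The statement of random recruitment and the age target also need reconciling.

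**What to change.** - **Section 4.1:** say whether recruitment is random within age strata, and give the intended split or sampling fractions.
- **Sections 4.4 and 7:** report each primary incidence separately for 60–74 and ≥75 with confidence intervals. Add an overall ≥60 rate in which the two age strata, pooled over countries, are weighted to the 60–74/≥75 population shares of the participating countries. Name the source of the shares and a suitable interval, such as a gamma or stratified bootstrap interval. Keep the crude rate beside it, labelled as the rate in the cohort.
- **Optional:** summaries of the primary endpoint by season and by country, as description only.

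The cost is a little extra analysis. Age should already be available from the baseline demographic data (section 5.3), and the population shares are public census figures. The interval for the weighted rate may be slightly wider than the crude one if incidence hardly differs by age (step 5). Stratum-specific intervals will be wide, more so for hospitalisation, where fewer events are likely.
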